6.7. Adverse events

Pertinent to safety assessment, the status of adverse events after the commencement of Genotropin therapy should be verified and the following information should be recorded. Adverse events should be verified in principle until the assessment period for each booklet is completed. Upon occurrence of any adverse event, the investigator shall provide appropriate intervention, promptly report to Sponsor in accordance with "Adverse event reporting" (Attachment 1), and follow up on the progress and outcome in principle until the symptoms disappear. Also, the investigator shall quickly notify Sponsor, "if a patient or the patient's partner conceives, or it has been found out that a patient or the patient's partner has conceived, whether adverse event has occurred or not," "if a serious adverse event occurred," and if any follow-up information thereto related has been obtained. Refer to "Adverse event reporting" (Attachment 1) for the details of procedures.

Furthermore, any occurrence of intrauterine exposure, or a serious adverse drug reaction or an adverse reaction not described in the package insert should be separately investigated as determined necessary by Sponsor.

- [1] Presence/absence of adverse event
- [2] Name of adverse event
- [3] Date of onset
- [4] Intervention
- [5] Seriousness
- [6] Outcome
- [7] Causal relation with Genotropin

[The following variables should be recorded if the adverse event is associated with abnormal test results, e.g., clinical laboratory]

- [8] Laboratory parameter

Ver.2

[9] Site reference

[10] Unit

[11] Date of measurement

[12] Result

Note: An adverse event is any untoward medical occurrence in a subject following Genotropin dose (including clinically significant change in laboratory test results); the event needs not necessarily to have a causal relationship with the treatment. A serious adverse event is any untoward medical occurrence that; Results in death; Is life-threatening (immediate risk of death), Requires inpatient hospitalization or prolongation of existing hospitalization; Results in persistent or significant disability/incapacity; Results in congenital anomaly/birth defect; or otherwise may result in medically important event or disorder.

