7. HANDLING OF MISSING VALUES

Any missing data on the seriousness, measures taken, and outcome of adverse events will be handled as “unknown” in summarizing data.

Measured values outside the acceptable range (Appendix 1) at each evaluation time point of the efficacy endpoints and clinical laboratory parameters will be handled as missing and missing data will not be imputed.

The procedure to handle uncleaned data is described below.

- Items with missing data: Missing data will be handled as missing (“unknown” for the category of classification variables) for both tabulation and listing.
- Items with inconsistent data: Inconsistent data will be handled as missing for both tabulation and listing. In this regard, however, a data handling list will be prepared separately.
- No signature: Descriptions in the report form without signature of the contract physician (or with signatures of other physicians than the contract physician) will be handled as missing for both tabulation and listing. No date or inconsistent date in the signature date section (eg, date of signature before or after the start date of treatment) will be considered to indicate that there is no signature on the report form.

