8. STATISTICAL METHODS AND ANALYSIS

8.1. Statistical Methods

8.1.1. Analysis of Continuous Data

Summary statistics (number of patients, mean, standard deviation, median, maximum value, and minimum value) will be calculated. Additionally, the first and third quartile points will be calculated as summary statistics for the efficacy endpoints.

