8.2.3.3. Other Endpoints

- **Laboratory test parameters**

The summary statistics of measured values of HbA1c at each evaluation point and change from the start of Genotropin will be calculated. The 95% confidence interval of the mean of the change will be calculated. The evaluation points are according to [Appendix A1.3](#) Definition of timing for visit 3.

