9. LISTS

The following lists will be prepared.

- Patient list.
- List of patients with adverse events.
- List of patients with adverse drug reactions.
- List of patients with adverse drug reactions excluded from safety analysis set.
- List of patients with serious adverse drug reactions.
- List of patients with serious adverse events.
- List of laboratory test parameters.

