11. APPENDIXES

11.1. Appendix 1: Details of Data Extraction

A1.1 DEFINITION OF TIMING FOR VISIT 1

Timing for visit	Endpoint	Definition [allowable range]
3 years	Height Height SDS Body weight SDS BMI SDS IGF-I SDS	3 years and 0 month to 3 years and 11 months
4 years	Height Height SDS Body weight SDS BMI SDS IGF-I SDS	4 years and 0 month to 4 years and 11 months
N years	Height Height SDS Body weight SDS BMI SDS IGF-I SDS	N years and 0 month to N years and 11 months

The measured value on the latest date will be used when the same patient receives more than one measurement during the same visit.

A1.2 DEFINITION OF TIMING FOR VISIT 2

Timing for visit	Endpoint	Definition [allowable range]
Start of Genotropin therapy	Height SDS Body weight SDS BMI SDS IGF-I SDS	90 days before the first date of treatment (the start date of treatment) to the start date of treatment for this investigation
Pubescence	Height SDS Body weight SDS BMI SDS IGF-I SDS	The date evaluated as the pubescence +90 days
At reaching adult height (near final height)	Height SDS Body weight SDS BMI SDS IGF-I SDS	The date evaluated to reach adult height (near final height) +90 days

The measured value on the earliest date will be used when the same patient receives more than one measurement during the same visit.

In this regard, all the data measured after reaching adult height (near final height) will be used if plots are prepared.

A1.3 DEFINITION OF TIMING FOR VISIT 3

Timing for visit	Endpoint	Definition [allowable range]
Start of Genotropin therapy	Laboratory test parameters Height SDS Height velocity Height velocity SDS Body weight SDS BMI SDS IGF-I SDS	90 days before the first date of treatment (the start date of treatment) to the start date of treatment for this investigation
1 year later	Laboratory test parameters Height SDS Height velocity Height velocity SDS Body weight SDS BMI SDS IGF-I SDS	365 ±90 days after the start of treatment
2 years later	Laboratory test parameters Height SDS Height velocity Height velocity SDS Body weight SDS BMI SDS IGF-I SDS	730 ±90 days after the start of treatment
N years later	Laboratory test parameters Height SDS Height velocity Height velocity SDS Body weight SDS BMI SDS IGF-I SDS	365 × N ±90 days after the start of treatment
Completion of Genotropin therapy	Laboratory test parameters Height SDS Height velocity Height velocity SDS Body weight SDS BMI SDS IGF-I SDS	Final date of treatment for this investigation (completion date of treatment) ±90 days

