Timing for visit	Endpoint	Definition [allowable range]
Completion of height follow-up	Height SDS Height velocity Height velocity SDS Body weight SDS BMI SDS	Completion date of height follow-up ± 90 days

The measured value on the earliest date will be used when the same patient receives more than one measurement during the same visit.

In this regard, all the data measured after the completion of height follow-up will be used if plots are prepared.

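### The visible HbA1c safety table has no worst-value or abnormal-count summary, and its visit rule can leave abnormal values out altogether

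*SAP*

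**What the plan says.** SAP 6.1 names laboratory tests as a safety endpoint. The only visible analysis of them is in SAP 8.2.3.3, which covers HbA1c: "The summary statistics of measured values of HbA1c at each evaluation point and change from the start of Genotropin will be calculated". It then adds: "The 95% confidence interval of the mean of the change will be calculated". SAP 8.1.1 fixes what a summary contains: "Summary statistics (number of patients, mean, standard deviation, median, maximum value, and minimum value) will be calculated".

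Two rules decide which values reach that table.

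- **Window.** Under SAP section 7, values of the efficacy endpoints and of "clinical laboratory parameters will be handled as missing and missing data will not be imputed" when they lie outside the range allowed for the evaluation point. For HbA1c that range is in Appendix A1.3. The first annual visit is "365 ±90 days after the start of treatment", later years follow the same pattern, and a further ±90-day window surrounds the end of treatment.
- **Selection within a window.** A1.3 states: "The measured value on the earliest date will be used when the same patient receives more than one measurement during the same visit".

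Two other routes could show an abnormal value. SAP section 9 plans a "List of laboratory test parameters". Protocol 6.7 defines adverse events as "including clinically significant change in laboratory test results", and SAP 8.2.3.2 tabulates adverse events by system organ class and preferred term. Section 8.2.3.4, the next item in the safety analysis, is redacted.

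**The concern.** A1.3 applies the same selection to growth measures and to a safety laboratory test. One value a year describes a growth curve well enough. For a safety test the values of most interest are the high ones, whenever they occur, and a rule based on calendar position can miss them. A raised HbA1c at month 6, or a second and higher value later in the same window, does not enter the annual rows of the table.

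The visible text also plans no count of children above a limit, no shift from baseline category and no highest post-start value. The one interval estimate is for the mean change, which barely moves when a few children worsen. Long-term safety is a stated objective and the results are meant for publication, so readers will want to know how many children became abnormal. The planned HbA1c table cannot tell them.

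**Working it through.** The plan states no figure to reproduce: 400 is a target without derivation, and SAP 4.1 sets no significance level.

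**1. Window coverage (A1.3)**
- Length of an annual window: 2 × 90 + 1 = 181 days. Share of a year: 181/365 = 49.6%.
- The first annual window opens on day 365 − 90 = 275, so days 1 to 274 lie in none.
- Gap between consecutive annual windows: 365 − 181 = 184 days.
- The completion-of-therapy window can recover values near the end of a child's treatment. Its contribution depends on when treatment ends and is not counted here.

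**2. Share of tests that reach the annual rows**

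Test frequency is not in the documents, so the intervals below are assumptions. Over three annual visits the span is 3 × 365 + 90 = 1,185 days, and the windows hold 3 × 181 = 543 of them (about 46%). At most one value per window is kept, so at most three per child.

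| Assumed test interval | Tests in 1,185 days | Share in a window | Share kept |
|---|---|---|---|
| 30 days | 39.5 | 46% | 3/39.5 = 8% |
| 91 days | 13.0 | 46% | 3/13.0 = 23% |
| 121 days | 9.8 | 46% | 3/9.8 = 31% |
| 182 days or longer | 6.5 or fewer | 46% | 46% |

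In the last row a window rarely holds more than one test, so the earliest-value rule costs nothing beyond the window rule. At quarterly testing it removes about half of the in-window values (46% falls to 23%). A simulation with evenly spaced tests at a random starting phase gave the same shares.

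**3. Sensitivity of the mean change**

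Assumptions: 400 children with paired values, k of them rising by d HbA1c points, and an SD of change between 0.2 and 0.4. None of these except the target of 400 is in the documents.
- Shift of the mean = k × d/400. With d = 1.0: 0.010 for k = 4 and 0.020 for k = 8. With d = 1.5: 0.004 for k = 1, 0.015 for k = 4 and 0.030 for k = 8.
- Half-width of the CI = 1.96 × SD/√400, which is 0.020, 0.029 and 0.039 for SDs of 0.2, 0.3 and 0.4.

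A rise of 1.5 points in 1% of children (k = 4) moves the mean by less than the half-width at every assumed SD. At 2% (k = 8) the shift exceeds the half-width at an SD of 0.2, is about equal to it at 0.3 and is below it at 0.4.

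**4. What a direct count would give**

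SAP 8.1.3 already specifies exact two-sided 95% intervals for proportions. For illustrative counts out of 400:
- 0 children: 0 to 0.92%
- 4 children (1%): 0.27 to 2.54%
- 8 children (2%): 0.87 to 3.90%

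**The case against.** A reader might infer that HbA1c is judged by the mean change alone, so that any abnormal value is averaged away. The documents do not support this. Under SAP 8.2.3.3 and 8.1.1 the table also gives the median, SD, minimum and maximum, for values and for changes. A large rise that is the selected value would normally show in the maximum, so step 3 of the working concerns one statistic among several.

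A reader might also infer that an omitted value can appear nowhere else. That too goes further than the text. A clinically significant laboratory change is an adverse event without a visit window, recorded with parameter, site reference, unit, date and result, and then tabulated and listed. Under Protocol 6.6 a laboratory abnormality given as the reason for stopping must also be entered as an adverse event. Section 7 makes off-window values missing at the evaluation point. It does not say that they leave the laboratory list.

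Three further points stand. The redaction of 8.2.3.4 means that the absence of a categorical analysis can be asserted only for the visible text. The investigation is not confirmatory and has no decision rule, so nothing in the plan says that a narrow interval will be read as proof of no effect on glucose metabolism. A highest value also depends on how often and how long a child is tested.

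These arguments narrow the point without removing it. The maximum is taken after selection, so it cannot show an omitted value, and it does not say how many children were abnormal or whether they were normal at the start. Adverse event reporting depends on each investigator's view of clinical significance. The content of the list is unspecified, and a list gives no rate.

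**Conclusion.** The point holds for the visible text of the plan. The HbA1c table has no worst-value or categorical summary, and its visit rule can omit abnormal values, including from the maximum. The certain part of the size is the window arithmetic: annual windows cover 49.6% of days and none of days 1 to 274, apart from what the completion window recovers. The added loss from keeping the earliest value runs from nothing at six-monthly or sparser testing to about half of in-window values at quarterly testing, and the actual frequency is unknown. The weak response of the mean rests on assumed rises, rates and SDs. How many abnormal values would in fact be lost cannot be determined from the documents.

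This is a gap in safety reporting that is worth closing before the final analysis. It does not show that the planned table is wrong, or that abnormal results would go unreported everywhere.

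**What to change.** Keep the table in 8.2.3.3 as planned. Add the following, using every HbA1c value recorded after the start of Genotropin, without window restriction:

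- each child's highest post-start value, summarised as in 8.1.1;
- a shift table from baseline category to highest post-start category, with a row for children without a baseline value;
- the number, percentage and exact 95% CI (8.1.3) of children newly above a threshold, among those at or below it at baseline with at least one later value.

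The sponsor should specify the threshold before the analysis. The plan cannot simply rely on site reference ranges, because Protocol 6.7 records these only when an adverse event involves an abnormal test, and Protocol 6.5 asks for results alone.

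Report the number of HbA1c tests per child and the length of follow-up beside these results, because the highest value tends to rise with both. That is the small downside of the measure. It would also help to state in section 9 whether the laboratory list includes off-window values.

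The cost is one decision on the threshold and a short additional output from HbA1c values already collected under Protocol 6.5. If the redacted 8.2.3.4 already contains this analysis, a cross-reference from 8.2.3.3 is sufficient.

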8.2.3.4. CCI

8.2.4. Efficacy Analysis

8.2.4.1. Change in Height

The summary statistics of measured values of height at each age will be calculated for the efficacy analysis set and eligible criteria set. The evaluation points are according to [Appendix A1.1](#) Definition of timing for visit 1. The change in height will be plotted with a solid line for individual male and female patients separately, with age on the horizontal axis and height on the vertical axis. On the plot, the plots of the standard height and standard height ± 1 SD, ± 2 SD, -2.5 SD, and -3 SD will be superimposed using a dotted line as a reference line for male and female patients, separately. The start of treatment will be indicated as ▲, pubescence as ●, and reaching adult height (near final height) as ▼. They will be plotted with a different dotted line from that used for the reference line after the completion/discontinuation of treatment.

The same calculation will be performed to prepare plots in the same manner for the set of patients who reached adult height (near final height) and set of patients not reached.

Additionally, a plot will be prepared with the change in the dose per week/kg after the start of Genotropin on the horizontal axis and change in height after the start of Genotropin on the vertical axis. The evaluation points of the change are according to [Appendix A1.3](#) Definition of timing for visit 3. Furthermore, a plot will be prepared with the change in the dose per

week/kg from the previous year on the horizontal axis and the change in height from the previous year on the vertical axis.

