5.4. Subsets

The following patient characteristics will be analyzed for efficacy by subsets.

- Age [less than 5 years, 5 years or older and less than 7 years, 7 years or older].
- Mother's birth history [the first childbirth / multipara].
- Presence/absence of GHD family history.
- Twin/multiplets.
- Fetus week number [less than 33 weeks, 33 weeks or older and less than 37 weeks, 37 weeks or older].

- Silver-Russell syndrome [yes, no].
- Period from the first date of treatment with growth hormone products including Genotropin to the pubescence [less than 2 years, 2 years or longer].

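### The table of height in cm by age has no split by sex, so its means and SDs depend on the sex mix of each age row

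*SAP*

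**What the plan says.** SAP 8.2.4.1 defines the table as follows: "The summary statistics of measured values of height at each age will be calculated for the efficacy analysis set and eligible criteria set". Its evaluation points come from Appendix A1.1. The next sentence turns to the figures: "The change in height will be plotted with a solid line for individual male and female patients separately". The standard-height curves laid over those figures are also sex-specific.

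Section 8.1.1 supplies the content of the table: "Summary statistics (number of patients, mean, standard deviation, median, maximum value, and minimum value) will be calculated". Quartiles are added for efficacy endpoints. There is no model and no adjustment.

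No other section supplies a split by sex:

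- Section 5.4 lists the subset factors: age, mother's birth history, family history of GHD, twin or multiple birth, gestational week, Silver-Russell syndrome, and time from first growth hormone treatment to pubescence. Sex is not among them.
- Section 8.2.4.8 applies those factors to the change in height SDS only, not to height in cm.

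In Appendix A1.1 each row covers a whole year of age, for example "3 years and 0 month to 3 years and 11 months". For repeated readings it says: "The measured value on the latest date will be used when the same patient receives more than one measurement during the same visit".

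**The concern.** The authors wrote a sex split where they wanted one, for the plots, and none for the table a sentence earlier. The SAP never uses the word pooled, but a programmer working from this text would produce one row per year of age with boys and girls together.

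Height is the first efficacy endpoint in section 6.2, and the protocol intends the results for publication. The SAP's own reference standard is by chronological age and gender, so a mean in cm over both sexes has no matching standard value. If the share of boys differs between rows, part of the difference between row means is composition and not growth. Mixing two distributions with different means also widens the SD.

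There is a design reason to expect drift in the later rows. SAP 5.3 sets the bone-age criterion for adult height at 17 years for males and 15 years for females. Height follow-up after treatment runs to adult height or to the end of the investigation (Protocol 5.4.3). If girls leave observation earlier, as these thresholds suggest they may, the older rows become more male. Those are also the rows where the sex difference in cm is likely to be largest.

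**Working it through.** The plan states no figure for this table, so there is nothing to reproduce. The inputs below are assumptions that show a range. None comes from the documents.

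**Sex mix**

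Inputs: the difference between boys' and girls' mean height in a row, d = 1, 5, 10 or 13 cm; a common within-sex SD, s = 4, 5 or 6 cm; and a change in male share of 0.10.

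- Shift in the pooled mean = d × 0.10.
- Pooled SD at equal numbers of boys and girls = √(s² + d²/4).

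| d (cm) | Shift per 10 points (cm) | Pooled SD, s = 4 | Pooled SD, s = 5 | Pooled SD, s = 6 |
|---|---|---|---|---|
| 1 | 0.1 | 4.03 | 5.02 | 6.02 |
| 5 | 0.5 | 4.72 | 5.59 | 6.50 |
| 10 | 1.0 | 6.40 | 7.07 | 7.81 |
| 13 | 1.3 | 7.63 | 8.20 | 8.85 |

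For example, with d = 10 and s = 6: √(36 + 25) = 7.81. With d = 13 and s = 6: √(36 + 42.25) = 8.85.

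The d = 1 line is meant for young children. A shift of 0.1 cm is lost against an assumed growth of 4-8 cm between successive rows. The d = 10 and d = 13 lines are meant for late adolescence, when growth is slowing. Criterion (a) for adult height in SAP 5.3 is an annual velocity below 2 cm. For children who meet it, a composition shift of 1.0-1.3 cm is half or more of the most they could grow in a year (1.0/2 = 50%, 1.3/2 = 65%).

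**Age at measurement within a row**

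The A1.1 window is a full year and the last reading is kept. Suppose a child has k readings spread uniformly over the age year. The last one then falls on average k/(k+1) of the way through: 0.50 for k = 1, 0.80 for k = 4 and 0.92 for k = 12. At an assumed velocity v, children measured four times exceed those measured once by v × 0.30. That is 1.2, 1.8 or 2.4 cm at 4, 6 or 8 cm/year. For twelve readings against one it is v × 0.423, or 1.7, 2.5 or 3.4 cm. Protocol 6.5 has the results of tests performed recorded and fixes no measurement frequency, so k is unknown. The effect shrinks as velocity falls. It is therefore largest where growth is fast and small in the late rows, where the sex effect is largest.

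**The case against.** The strongest reply is that the plan already covers the comparison that matters. Section 8.2.4.2 requires height SDS at each age in the same two sets with the same A1.1 rows, and section 6.2 standardises SDS for chronological age and gender. The 8.2.4.1 plots are split by sex and carry the sex-specific standard curves. Section 8.2.2 tabulates gender for each analysis set. Sections 4.1 and 4.2 make the investigation non-confirmatory with no decision rules, and nothing is decided from the cm table. All of this stands and limits the weight of the point. It does not make the cm table readable by itself: gender is tabulated per set and not per age row, and SDS removes the dependence on timing only if it is computed at the exact age on the measurement date.

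Three stronger inferences are tempting, and the documents do not support them.

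- *A reader might infer that the SAP will publish a mean adult height in cm over both sexes.* Reaching adult height is an evaluation point only in Appendix A1.2, which lists height SDS and other SDS endpoints but not height in cm. The 8.2.4.1 sentence on the adult-height and not-reached sets ties the repeated calculation to preparing plots. Whether numeric tables are meant for those sets is unclear.
- *A reader might infer that the latest-reading rule is an error because A1.2 and A1.3 take the earliest.* The rule is explicit and reproducible, and the A1.1 windows are of a different kind, by age and not around a treatment or event date. Taking the reading nearest mid-year would be a preference, not a correction.
- *A reader might infer a general timing bias of 2-4 cm.* An average last reading at N + 0.9 years needs about nine readings a year, since 9/10 = 0.9. The documents give no such frequency.

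**Conclusion.** The point holds as a cheap improvement to one descriptive table. As written, 8.2.4.1 yields means and SDs of height in cm that depend on the sex mix of each age row. On the assumed inputs the effect is negligible in young children. In late-adolescent rows it is about 1.0-1.3 cm per 10-point change in male share, with a pooled SD of 7.8-8.9 cm where the within-sex SD is 6 cm. These figures rest on a 10-13 cm sex difference, equal SDs in the two sexes and, for the SD, equal numbers of boys and girls. That the later rows become more male is a possibility suggested by the sex-specific bone-age thresholds. The documents do not show that it will happen.

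It would go too far to say that the efficacy analysis is compromised. The analyses of change with confidence intervals use height SDS, height velocity and other standardised measures, and the height SDS table by age carries the main message.

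**What to change.** In SAP 8.2.4.1, state that the summary of height in cm by age is produced separately for males and females in the efficacy analysis set and the eligible criteria set. State also whether numeric tables are intended for the adult-height and not-reached sets and, if so, apply the same split there. Print the mean exact age at measurement in each row, so that a reader can see where in the year the readings fall. The A1.1 selection rule can stay as it is.

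Sex, date of birth and height are already collected, and mean age follows from the measurement dates. The programming change is one stratifying variable and one extra column. The cost is more table pages and smaller cells, and some late-age rows by sex may hold few patients. The number of patients is already among the planned statistics, so thin rows will be visible.
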